# **Protocol Synopsis**

Title B-Lymphocyte Immunotherapy in Islet Transplantation:

Toward Calcineurin-Inhibitor Free Immunosuppression

**Short Title** B-Lymphocyte Immunotherapy in Islet Transplantation

**Clinical Phase** Phase 2

**IND Sponsor** DAIT/NIAID/NIH

**BB-IND 9336 IND Number** 

**Activation Date:** November 2006

12 subjects **Accrual Objective** 

**Accrual Period** 24 months

**Study Duration** 12 months after final transplant

Open-label, single-center, prospective single arm study. **Study Design** 

**Treatment Description** Islet transplantation will be performed under an experimental

> immunosuppression arm. The experimental immunosuppression will consist of the anti-B lymphocyte agent rituximab in combination with

Thymoglobulin® (daclizumab or basiliximab instead of Thymoglobulin® for the 2nd and 3rd transplants, if applicable) for induction and sirolimus alone for maintenance, a calcineurin-inhibitor

free regimen.

#### **Study Design**

This is an open-label, prospective, single-arm, single-center trial.

Objectives of this study include gaining experience with the experimental immunosuppression treatment regimen as well as to determine the proportion of subjects with insulin independence on this experimental regimen. Should these subjects demonstrate a very high rate of insulin independence at  $75 \pm 5$  days post-transplant (a rate of 40% or higher would be considered high by current standards), then this treatment may be considered for further study.

There is a larger parallel study with additional centers and more subjects (CIT-07) where subjects are treated with a standard Islet Transplant immunosuppression regimen. Subjects will be randomized to receive either the standard immunosuppression regimen under CIT-07 or the experimental immunosuppression in this protocol (CIT-05) at the time an islet preparation meets release criteria. The randomization will provide a mechanism for balance between the two studies and provide an objective selection of subjects to the two studies.

# **Primary Endpoint**

The primary endpoint will be insulin-independence at  $75\pm 5$  days following the first islet transplant.

#### **Primary Analysis**

The primary analysis will be to provide an estimate of the proportion of subjects with insulin independence and a corresponding 95% confidence interval

# **Secondary Endpoints**

# **Efficacy Endpoints**

At  $75 \pm 5$  days following the first and final islet transplant:

- Proportion of insulin-independent subject
- The percent reduction in insulin requirements
- HbA1c
- Mean amplitude of glycemic excursions (MAGE)
- Glycemic lability index (LI)
- Ryan hypoglycemia severity (HYPO) score
- Basal (fasting) and 90-min glucose and c-peptide derived from the mixed-meal tolerance test (MMTT)
- β-score
- C-peptide: (glucose X creatinine) ratio
- Acute insulin response to glucose (AIRglu), insulin sensitivity, and disposition index derived from the insulin-modified frequently-sampled intravenous glucose tolerance (FSIGT) test
- Glucose variability and hypoglycemia duration derived from the continuous glucose monitoring system®
- Quality of life measures

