#### 3.1.1 Secondary Endpoints

#### **Efficacy Endpoints**

At  $75 \pm 5$  days following the first and final transplant(s):

- The proportion of insulin-independent subjects
- The percent reduction in insulin requirements
- HbA1c
- MAGE
- LI
- Ryan hypoglycemia severity (HYPO) score
- Basal (fasting) and 90-min glucose and c-peptide derived from the mixed-meal tolerance test (MMTT)
- β-score
- C-peptide: (glucose X creatinine) ratio
- Acute insulin response to glucose (AIRglu), insulin sensitivity, and disposition index derived from the insulin-modified frequently-sampled IV glucose tolerance (FSIGT) test
- Glucose variability6 and hypoglycemia duration derived from the CGMS

• Quality of life (QOL) measures

If a third transplant occurs less than 75 days after the second transplant, the 75 day endpoint data for the second transplant will not be collected.

At  $365 \pm 14$  days following the first transplant

- The proportion of subjects with an HbA1c <7.0% at Day 365 AND free of severe hypoglycemic events from Day 28 to Day 365 inclusive
- The proportion of subjects receiving a second islet transplant
- The proportion of subjects receiving a third islet transplant

A severe hypoglycemic event is defined as an event with one of the following symptoms: memory loss; confusion; uncontrollable behavior; irrational behavior; unusual difficulty in awakening; suspected seizure; seizure; loss of consciousness; or visual symptoms, in which the subject was unable to treat him/herself and which was associated with either a blood glucose level <54 mg/dL [3.0 mmol/L] or prompt recovery after oral carbohydrate, IV glucose, or glucagon administration.

At  $365 \pm 14$  days following the first and final islet transplant:

- The proportion of insulin-independent subjects
- The percent reduction in insulin requirements
- HbA1c
- MAGE
- LI
- Clarke score
- HYPO score
- Basal (fasting) and 90-min glucose and c-peptide (MMTT)
- β-score
- C-peptide: (glucose X creatinine) ratio
- AIRglu insulin sensitivity, and disposition index derived from the FSIGT test
- CGMS
- OOL
- The proportion of subjects receiving a second islet transplant
- The proportion of subjects receiving a third islet transplant
- The rate of subjects with an HbA1c  $\leq$ 7.0% and free of severe hypoglycemic events)

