# 10.2 Study Endpoint Assessment

# 10.2.1 Primary Endpoint

The primary objective of the analysis is to estimate the rate of insulin independence at 75 days after the first Islet Transplant among those in the study. The primary endpoint is insulin independence (yes/no) at day 75 after Islet Transplant as defined in section 3.1. The primary analysis will compute an exact binomial estimate and a 95% confidence interval for the true rate.

The primary endpoint should be available for all randomized subjects. An exception will be if a death occurs or if the subject withdraws consent to be followed, in these cases the endpoint will be classified as failure to achieve insulin independence. Should the endpoint not be evaluated for a particular individual for other reasons, a failure will be imputed unless an evaluation is done at a time longer than 75 days after transplant and before an additional islet transplant, in which case that later value will be imputed. All imputations will be reported with the primary analysis.

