# 10.2.2 Secondary Endpoint

As a secondary analysis the proportion of subjects with insulin independence at 75 days after transplant will be compared to the proportion of subjects with insulin independence at the University of Pennsylvania in the CIT-07 study using an exact test for two proportions. The same proportion will also be compared to pooled analysis of all subjects in the CIT-07 study from the four CIT centers (see the Statistical Analysis Plan, SAP).

Dichotomous variables such as HbA1c classified as normal ( $\leq$ 7.0%) and non-normal ( $\geq$ 7.0%) will be analyzed in a manner similar to the primary analysis. Continuous variables such as HbA1c, AIRg and c-peptide response will be examined for normality of the distribution and if there is no compelling evidence that the distribution is non-normal, will be analyzed by computing the mean and calculating a 95% confidence interval using the student's t-distribution

If there is compelling evidence that the normal distribution does not apply a logarithmic, square root or other transformation will be done before analyzing the data. An estimate and a 95% confidence interval for each response will be calculated. In addition, the responses will be

compared to the responses in subjects at the University of Pennsylvania in CIT-07 (using an exact test for two proportions, or a t-test, possibly after transformation, for continuous variables).

The additional hypothesis generating endpoints of 3.1.2 and the additional endpoints in 3.1.3 will be analyzed similarly and all the data will be subject to exploratory analysis. For variables that are collected at regular follow up visits, regression models for longitudinal data will be used to examine the responses over time for both dichotomous and continuous variables.

Values will not be imputed for missing secondary endpoints. The frequency of missing data will be reported.

There are a very large number of secondary endpoints. By examining multiple secondary endpoints it is likely that some variables will be found significantly different between the subjects in this study and those from the University of Pennsylvania in CIT-07, but these findings may be Type I errors. Appropriate qualifiers will be reported with any findings which are nominally significant at the 0.05 level or less and such results should be interpreted with extreme caution.

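### Day 75 insulin independence after the first transplant is listed as both primary and secondary endpoint, and the two sections handle its missing values differently

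*Protocol*

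**What the plan says.** **Primary endpoint.** The Synopsis and Section 3.1 define it: "The primary endpoint will be insulin-independence at" 75 ± 5 days after the first islet transplant.

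**Secondary endpoints.** The Synopsis list for 75 ± 5 days after the first and final transplant opens with "Proportion of insulin-independent subject". Section 3.1.1 does the same under the same time point: "The proportion of insulin-independent subjects".

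**Missing data, primary (Section 10.2.1).** After a death or withdrawal of consent, "in these cases the endpoint will be classified as failure to achieve insulin independence". If the endpoint is not evaluated for any other reason, "a failure will be imputed unless an evaluation is done at a time longer than 75 days after transplant" and before a further islet transplant; that later value is then used.

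**Missing data, secondary (Section 10.2.2).** "Values will not be imputed for missing secondary endpoints"; only the frequency of missing data is reported. No exception is made for the item that is also the primary endpoint. The same section says that dichotomous variables "will be analyzed in a manner similar to the primary analysis".

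**Comparison with CIT-07.** It is specified in Section 10.2.2: "As a secondary analysis the proportion of subjects with insulin independence at 75 days after transplant will be compared" with CIT-07 subjects at the same university and then with the pooled CIT-07 subjects. No missing-data rule is named for it.

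**The concern.** One outcome, at one visit, in the same subjects, appears under two endpoint labels, and each label has its own missing-data rule. The first-transplant half of the secondary item is the primary endpoint. For a subject who receives only one transplant, the after-final half is also that visit. Two analysts could each follow the text and report different proportions.

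The difference has a direction. A subject who dies or withdraws stays in the denominator as a failure under 10.2.1. Without imputation, that subject has no value to count under 10.2.2. The after-final rate could therefore exceed the after-first rate although nobody was transplanted again, and a reader could take this for a benefit of further transplants. In a study of 12, one or two subjects are enough to show.

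**Working it through.** **Inputs from the protocol.** The sample size is 12 (Section 10.4), and the intervals are exact binomial 95% intervals (Sections 10.2.1 and 10.4).

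**Assumption.** The number missing, m, is set to 1, 2 or 3, because the protocol gives no dropout rate. Each missing subject is one whom 10.2.1 would score as a failure: a death, a withdrawal of consent, or a missed evaluation with no usable later value.

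**Step 1: reproduce the protocol's own figure.** For x successes in n subjects, the Clopper-Pearson limits are:
- lower = 0.025 quantile of Beta(x, n − x + 1)
- upper = 0.975 quantile of Beta(x + 1, n − x)

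For 6 of 12 this gives 0.2109 to 0.7891. Section 10.4 prints 0.21 to 0.79, so the method agrees.

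**Step 2: the two rules.**
- 10.2.1: rate = x/12, whatever m is.
- 10.2.2 read literally: rate = x/(12 − m).
- Ratio of the second to the first = 12/(12 − m): 12/11 = 1.09, 12/10 = 1.20, 12/9 = 1.33.

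**Step 3: results.**

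| Successes | Missing (assumed) | Rule of 10.2.1 | Observed subjects only |
|---|---|---|---|
| 4 | 1 | 4/12 = 33.3% (0.099–0.651) | 4/11 = 36.4% (0.109–0.692) |
| 4 | 2 | 4/12 = 33.3% (0.099–0.651) | 4/10 = 40.0% (0.122–0.738) |
| 4 | 3 | 4/12 = 33.3% (0.099–0.651) | 4/9 = 44.4% (0.137–0.788) |
| 6 | 1 | 6/12 = 50.0% (0.211–0.789) | 6/11 = 54.5% (0.234–0.833) |
| 6 | 2 | 6/12 = 50.0% (0.211–0.789) | 6/10 = 60.0% (0.262–0.878) |
| 6 | 3 | 6/12 = 50.0% (0.211–0.789) | 6/9 = 66.7% (0.299–0.925) |

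If none of the 12 had a second transplant, the second row would be reported as 33% after the first transplant (primary) and 40% after the final transplant (secondary), from the same 12 visits.

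**Step 4: limit on the direction.** The ratio is never below 1 when the missing subjects are failures under 10.2.1; it has no effect when m = 0 or x = 0. The later-evaluation exception can reverse the direction. Suppose there are 4 observed successes and one subject whose Day 75 visit was missed but whose later evaluation was a success. Then 10.2.1 gives 5/12 = 41.7%, and observed subjects only gives 4/11 = 36.4%. Deaths and withdrawals of consent have no such exception.

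**The case against.** **A harmonised reading is available.** Section 10.1 bases all efficacy analyses on intention to treat and keeps every transplanted subject in. Section 10.2.2 treats dichotomous variables like the primary analysis. Section 10.2.1 also uses two verbs: death and withdrawal are classified as failure, while only other missing values are imputed, so a ban on imputation need not undo the classification. This has some force. The protocol nowhere says that such subjects are dropped; that follows from not imputing. But the classification is stated for the primary endpoint only, the no-imputation sentence is explicit and has no exception, and nothing ranks the general statements above it. The verb distinction would also leave the other missing values in conflict.

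**A reader might infer that the CIT-07 comparison drops deaths and withdrawals.** The documents do not support this. The Synopsis (Secondary Analyses) says that primary and secondary endpoints alike are compared with CIT-07. Section 2.1 calls the comparison a secondary analysis, and Section 10.5 calls the quantity compared the primary outcome. It is best read as a secondary analysis of the primary endpoint, so the rule for missing secondary endpoints is not clearly attached to it. What remains is that it sits in 10.2.2 beside the no-imputation sentence with no rule named. The choice could matter. With an assumed CIT-07 result of 9/12 and none missing there, 3 successes and 3 missing here give a two-sided Fisher p of 0.039 as 3/12 and 0.087 as 3/9. Those counts are chosen for illustration; the protocol gives no CIT-07 result.

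**A reader might infer that the 40% mark becomes ambiguous.** It does not. The mark in the Synopsis and Section 3 concerns Day 75 insulin independence, which is estimated under 10.2.1. It says only that the regimen may then be considered for further study.

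**Part of this could be left to the SAP.** The SAP is not at hand and may settle the comparison in detail. The conflict itself is in the protocol, which states both rules.

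**Conclusion.** The inconsistency is real and its reach is limited. The primary analysis is unambiguous and does not change. Affected are the duplicated after-first proportion and, for subjects transplanted once, the after-final proportion. Read literally, these are inflated by a factor of 12/(12 − m): about 9%, 20% or 33% in relative terms for 1, 2 or 3 missing subjects who would be failures under 10.2.1. The size depends entirely on the assumed number missing; with complete data the rules agree. For the CIT-07 comparison, the finding is only that its rule should be stated. The point is worth correcting because the change costs little and removes a choice of denominator that could otherwise be made after the outcomes are known.

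**What to change.** 1. In the Day 75 secondary lists (Synopsis and Section 3.1.1), keep insulin independence for the final transplant only, so that the after-first proportion is the primary endpoint and nothing else.
2. Add to Section 10.2.2: *The missing-data rule of Section 10.2.1, including its exception for a later evaluation before an additional transplant, applies to every analysis of Day 75 insulin independence. This includes the proportion after the final transplant and the comparison with CIT-07, in which CIT-07 subjects are handled in the same way.*

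The cost is a few lines of wording and no new data. The secondary rates may come out slightly less favourable than they would over observed subjects only. Equal handling in the comparison requires the same rule to be applied to the CIT-07 data.

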# At $365 \pm 14$ days following the first islet transplant:

- The proportion of subjects with an HbA1c <7.0% at Day 365 AND free of severe hypoglycemic events from Day 28 to Day 365 inclusive
- The proportion of subjects receiving a second islet transplant
- The proportion of subjects receiving a third islet transplant

# At $365 \pm 14$ days following the first and final islet transplant:

- The proportion of insulin-independent subjects
- The percent reduction in insulin requirements
- HbA1c
- MAGE
- LI
- Clarke hypoglycemia awareness score
- HYPO score
- Basal (fasting) and 90-min glucose and c-peptide (MMTT)
- β-score
- C-peptide: (glucose X creatinine) ratio
- Acute insulin response to glucose (AIRglu), insulin sensitivity, and disposition index derived from the insulin-modified frequently-sampled intravenous glucose tolderance (FSIGT) test.
- QOL (DQOL, HSQ 2.0, HFS)
- The proportion of subjects receiving a second islet transplant
- The proportion of subjects receiving a third islet transplant
- The proportion of subjects with a HbA1c ≤7.0% and free from severe hypoglycemic events

# **Safety Endpoints**

At  $75 \pm 5$  and  $365 \pm 14$  days following the first and final islet transplant:

- The incidence and severity of adverse events related to the islet transplant procedure including: bleeding (>2 g/dL decrease in hemoglobin concentration); segmental portal vein thrombosis; biliary puncture; wound complication (infection or subsequent hernia); and increased transaminase levels (>5 times upper limit of normal [ULN])
- The incidence and severity of adverse events related to the immunosuppression including: allergy; reduction in GFR; increase in urinary albumin excretion; addition or intensification of anti-hypertensive therapy; addition or intensification of anti-hyperlipidemic therapy; oral ulcers; lower extremity edema; gastrointestinal toxicity; neutropenia, anemia, or thrombocytopenia; viral, bacterial, or fungal infections; and benign or malignant neoplasms
- The incidence of a change in the immunosuppression drug regimen
- The incidence of immune sensitization defined by detecting anti-HLA antibodies not present prior to transplantation

At  $365 \pm 14$  days following the first islet transplant:

• The incidence of worsening retinopathy as assessed by change in retinal photography

# **Insulin Independence Definition**

Islet transplant recipients will be considered insulin-independent with full islet graft function if they are able to titrate off insulin therapy for at least 1 week and all of the following criteria are met:

- HbA1c  $\leq$ 7.0% or a  $\geq$ 2.5% decrease from baseline;
- fasting capillary glucose level should not exceed 140 mg/dL (7.8 mmol/L) more than three times in the past week (based on measuring capillary glucose levels a minimum of 7 times in a seven day period);
- 2-hour post-prandial capillary glucose should not exceed 180 mg/dL (10.0 mmol/L) more than three times in the past week (based on measuring capillary glucose levels a minimum of 21 times in a seven day period);
- fasting serum glucose level ≤126 mg/dL (7.0 mmol/L); if the fasting serum glucose level is >126 mg/dL (7.0 mmol/L), it must be confirmed in an additional one out of two measurements;
- evidence of endogenous insulin production defined as fasting or stimulated c-peptide levels ≥0.5 ng/mL (0.16 nmol/L).

## **Secondary Analyses**

The secondary analyses will compare the primary and secondary endpoints in this study to the corresponding outcomes in the CIT-07 study. Estimates and 95% confidence intervals will also be calculated.

# Severe Hypoglycemic Event Definition

A severe hypoglycemic event is defined as an event with one of the following symptoms: memory loss; confusion; uncontrollable behavior; irrational behavior; unusual difficulty in awakening; suspected seizure; seizure; loss of consciousness; or visual symptoms, in which the subject was unable to treat him/herself and which was associated with either a blood glucose level <54 mg/dL (3.0 mmol/L) or prompt recovery after oral carbohydrate, IV glucose, or glucagon administration.

#### **Inclusion Criteria:**

Patients who meet *all* of the following criteria are eligible for participation in the study:

1. Male and female patients age 18 to 65 years of age.

- 2. Ability to provide written informed consent.
- 3. Mentally stable and able to comply with the procedures of the study protocol.
- 4. Clinical history compatible with T1D with onset of disease at <40 years of age and insulindependence for ≥5 years at the time of enrollment, and a sum of patient age and insulin dependent diabetes duration of ≥28 years.
- 5. Absent stimulated c-peptide (<0.3ng/mL) in response to a mixed meal tolerance test (MMTT; Boost® 6 mL/kg body weight to a maximum of 360 mL; another product with equivalent caloric and nutrient content may be substituted for Boost) measured at 60 and 90 min after the start of consumption.
- 6. Involvement in intensive diabetes management defined as self monitoring of glucose values no less than a mean of three times each day averaged over each week and by the administration of three or more insulin injections each day or insulin pump therapy. Such management must be under the direction of an endocrinologist, diabetologist, or diabetes specialist with at least 3 clinical evaluations during the 12 months prior to study enrollment.
- 7. At least one episode of severe hypoglycemia, defined as an event with one of the following symptoms: memory loss; confusion; uncontrollable behavior; irrational behavior; unusual difficulty in awakening; suspected seizure; seizure; loss of consciousness; or visual symptoms, in which the subject was unable to treat him/herself and which was associated with either a blood glucose level <54 mg/dL [3.0 mmol/L] or prompt recovery after oral carbohydrate, IV glucose, or glucagon administration, in the 12 months prior to study enrollment.
- 8. Reduced awareness of hypoglycemia as defined by a Clarke score of 4 or more OR a HYPO score greater than or equal to the 90th percentile (1047) during the screening period and within the last 6 months prior to randomization;

#### OR

Marked glycemic lability characterized by wide swings in blood glucose despite optimal diabetes therapy and defined by an LI score greater than or equal to the 90th percentile (433 mmol/L²/h·wk⁻¹) during the screening period and within the last 6 months prior to randomization;

#### OR

A composite of a Clarke score of 4 or more and a HYPO score greater than or equal to the 75th percentile (423) and an LI greater than or equal to the 75th percentile (329) during the screening period and within the last 6 months prior to randomization.

